# 4.4.4 Details of place of residence, work, recent travel history and risk behaviours of forest goers in order to improve the understanding of high risk groups, locations of malaria transmission and possible routes spread of malaria and artemisinin resistance.

Data on the place of residence and work have been presented in table 1 above. The travel history and risk behaviours during the course of prophylaxis will be presented descriptively by study arm in table 5 below.

Table 5 Travel history and risk behaviours during the course of prophylaxis

	AL	Multivitamin	p-value
	(N=XXX)	(N=XXX)	
Recent travel history, n(%)			
Travel destination			
Stung Treng	XX (XX.X)	XX (XX.X)	0.XXX
Siem Pang	XX (XX.X)	XX (XX.X)	0.XXX
Others	XX (XX.X)	XX (XX.X)	0.XXX
Travelling reasons			
XX	XX (XX.X)	XX (XX.X)	0.XXX
XX	XX (XX.X)	XX (XX.X)	0.XXX
Risk behaviours			
Forest visit, n(%)	XX (XX.X)	XX (XX.X)	0.XXX
How many nights spent in the forest, median (IQR)	XX.X (XX.X - XX.X)	XX.X (XX.X - XX.X)	0.XXX
How many days spent in the forest, median (IQR)	XX.X (XX.X - XX.X)	XX.X (XX.X - XX.X)	0.XXX

Duration of travelling (days), median (IQR)	XX.X (XX.X - XX.X)	XX.X (XX.X - XX.X)	0.XXX
How many other people did you travel with? , median (IQR)	XX.X (XX.X - XX.X)	XX.X (XX.X - XX.X)	0.XXX
Sleep in the forest, n(%)	XX (XX.X)	XX (XX.X)	0.XXX
Bednet use, n(%)	XX (XX.X)	XX (XX.X)	0.XXX
Hammock net use, n(%)	XX (XX.X)	XX (XX.X)	0.XXX
Repellent spray or cream use, n(%)	XX (XX.X)	XX (XX.X)	0.XXX
Mosquito coil use, n(%)	XX (XX.X)	XX (XX.X)	0.XXX
Use anything else to protect you from mosquito bites, n(%)	XX (XX.X)	XX (XX.X)	0.XXX
Take any other antimalaria medicine, n(%)	XX (XX.X)	XX (XX.X)	0.XXX
Use anything else to protect you from getting malaria, n(%)	XX (XX.X)	XX (XX.X)	0.XXX

#### 4.4.5 Adverse events and serious adverse events by study arms during the course of prophylaxis.

Adverse events will be graded according to Common Terminology Criteria for Adverse Events (CTCAE) Version 5.0 November 2017.

All adverse event summaries will refer to treatment emergent adverse events, i.e. adverse events that newly started or increased in intensity after the study drug administration. AE summaries will be generated for all AEs that occurred after study drug administration, until the end of the study.

Incidence of adverse events and serious adverse events by study arms during the course of prophylaxis will be presented in the table 6a below. AE intensity and relationship to study drug wil be presented as in tables 6b and 6c. Graphical presentations might be considered when presenting these.

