6.6. Follow-up

Participants will be asked to return for a follow-up assessment any time from 28 to 35 days after commencing prophylaxis. This will be regardless of the duration of their visit to the forest or the number of times they visited it in that period. At this assessment, they will be interviewed about how long they spent in the forest, where they went, why, who they travelled with and about risk factors for infection. Brief physical examinations, vital sign and symptom questionnaire will be performed. They will also be asked to report any diagnostic tests and/or treatment for malaria during the preceding 28-35 days.

Blood sampling at follow-up

At each follow-up visit, the following blood will be taken:

All individuals:

- Parasite PCR (Up to 1 ml).

- Dried blood spot for lumefantrine level (0.2 ml)

In those with confirmed clinical malaria at any time point between enrolment and follow-up:

- Dry blood blots (0.4 ml, 3 spots) collected on filter papers for:
 - o Parasite DNA genotyping for genetic markers of antimalarial resistance.
 - o Parasite whole genome sequencing and barcoding to identify geographical origin of parasites and compare genotypes to identify persistent infections.

In individuals who are planning to return again to the forest within the following 28 days after the follow up visit, they will be asked to continue their weekly prophylaxis according to the original treatment allocation on enrolment. They will then be asked to return for a second follow-up visit a further 28 to 35 days later when the above procedure will be repeated. This will be repeated one more time. If the person cannot be followed up within the scheduled period, e.g. because they do not return from the forest in time, then they will be followed up at the first opportunity and this will be recorded in the CRF.

Thus individuals may take prophylaxis continuously for a maximum of 3 periods of 28-35 days in the forest plus 4 weeks after returning totaling 112 days. The choice of study medication for each individual will follow the initial assignment on enrolment throughout the follow-up period.

In those who do not declare an intention to return to the forest within 28 days at any follow-up visit, no further follow-up visits will be offered at that time but they will be asked to complete 4 weeks of prophylaxis following their last day in the forest as post-exposure prophylaxis.

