8. SAFETY REPORTING

This trial will use drugs that have either been registered or evaluated extensively. To add to the evidence base for safety of AL as prophylaxis, we will record and review all Adverse Events (AEs) and Serious Adverse Events (SAEs) that are reported to occur in the study.

A symptom questionnaire will be performed on enrolment and at each subsequent follow-up visit to the health care center, to aid in the identification of adverse events. In addition, enrolled individuals will be encouraged to promptly report any unexpected symptoms or illnesses between follow-up visits to the study team.

The investigator is responsible for the detection and documentation of events meeting the criteria and definition of an adverse event (AE) or serious adverse event (SAE), as provided in this protocol.

All SAEs and AEs will be promptly documented from the moment of drug administration in the study to discontinuation of the participant from study participation. Any events occurring between screening and drug administration will be considered as baseline, preexisting conditions.

All adverse events must be recorded in the AE/SAE CRF. To avoid colloquial expressions, the adverse event should be reported in standard medical terminology. Whenever possible, the adverse event should be evaluated and reported as a diagnosis rather than as individual signs or symptoms. If a definitive diagnosis is not possible, the individual symptoms and signs should be recorded. Whenever possible, the aetiology of the abnormal findings will be documented on the CRF. Any additional relevant laboratory results obtained by the Investigator during the course of this study will be recorded on the CRF.

If the event meets the criteria for “serious”, the SAE must be reported to the PAL-Cambodia safety team within 24 hours from the time that the event was identified. If further data is required, additional documentation can be submitted. All SAEs must be followed until resolution, or until the SAE is deemed permanent or leads to death.

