9.2.3 Safety analysis

Safety analyses will be based on the whole population that get administered the study drug. Safety and tolerability of ACT versus multivitamin will be assessed by comparing the frequency (%) of adverse events and serious adverse events, with particular attention to abdominal pain, appetite perturbation, using the Fisher's exact test. Safety data will be presented in tabular and/or graphical format and summarised descriptively. Any clinically relevant abnormalities or values of potential clinically concern will be described. Participants will be analysed according to an intention to treat and a per protocol method where appropriate.

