#### Table 6a Adverse events

	Adverse event, n (%)		p-value
	AL	AL Multivitamin	
	(N=XXX)	(N=XXX)	
Signs and symptoms			
Headache	XX (XX.X)	XX (XX.X)	0.XXX
Loss of appetite	XX (XX.X)	XX (XX.X)	0.XXX
Dizziness	XX (XX.X)	XX (XX.X)	0.XXX
Fatigue	XX (XX.X)	XX (XX.X)	0.XXX
Joint pain	XX (XX.X)	XX (XX.X)	0.XXX
Muscle pain	XX (XX.X)	XX (XX.X)	0.XXX
Abdominal pain	XX (XX.X)	XX (XX.X)	0.XXX
Nausea	XX (XX.X)	XX (XX.X)	0.XXX
Vomiting	XX (XX.X)	XX (XX.X)	0.XXX
Diarrhoea	XX (XX.X)	XX (XX.X)	0.XXX
Itching	XX (XX.X)	XX (XX.X)	0.XXX

Cough	XX (XX.X)	XX (XX.X)	0.XXX
Fever	XX (XX.X)	XX (XX.X)	0.XXX
Serious adverse events	XX (XX.X)	XX (XX.X)	0.XXX

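### SAP Table 6a compares symptom percentages over one N per arm, although time on drug and the number of symptom questionnaires depend on a declaration made after randomisation with the arm known

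*SAP*

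**What the plan says.** - **Measure.** SAP 4.4.5: "Incidence of adverse events and serious adverse events by study arms during the course of prophylaxis will be presented in the table 6a below". The columns of Table 6a are headed "Adverse event, n" (%), with one N per arm and a p-value. The rows are 13 individual symptoms and one line for serious adverse events (SAEs). There is no row for any adverse event (AE), no person-time and no split by month, whereas efficacy Tables 2 and 3 are split by month.
- **Test and population.** Protocol 9.2.3: "Safety analyses will be based on the whole population that get administered the study drug". Safety is judged by "comparing the frequency (%) of adverse events and serious adverse events", using Fisher's exact test.
- **Window.** SAP 4.4.5 also says "AE summaries will be generated for all AEs that occurred after study drug administration, until the end of the study". This is a different window from the course of prophylaxis, and both vary in length between people.
- **How AEs are found.** Protocol 8: "A symptom questionnaire will be performed on enrolment and at each subsequent follow-up visit to the health care center". Appendix 1 places the post-dose questionnaires at D28–35, D56–63 and D84–91. Between visits, "enrolled individuals will be encouraged to promptly report any unexpected symptoms or illnesses between follow-up visits to the study team".
- **Who is seen again.** Protocol 6.6 gives the rule in a sentence that begins "In those who do not declare an intention to return to the forest within 28 days at any follow-up visit, no further follow-up visits will"; for this group, visits end there. Those who do plan another trip continue the allocated product and have a further visit, up to three in all. Protocol 6.3 states that the trial is open label.

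**The concern.** The chance that a symptom is ever recorded rises with the number of periods on study and the number of times the participant is asked. Both are settled after randomisation, by a declaration that can be influenced by knowing the arm. A percentage over everyone given study drug therefore reflects two things: how often the symptom occurs per period, and how many periods the arm contributed.

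At stake is secondary endpoint 5, the incidence of AEs by arm. A row of Table 6a could show a significant difference when the risk per period is the same in both arms, and nothing in the table would let a reader separate continuation from drug effect. The direction cannot be predicted. Participants on artemether-lumefantrine (AL) might continue less because of tolerability, or more because they feel protected.

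**Working it through.** **Inputs.** The documents give no AE rate and no continuation rate, so there is no stated safety figure to reproduce. The only checkable figure, 1,605 per arm for 5% v 3% positivity, reproduces with a continuity correction (1,506 without). It concerns efficacy, and nothing below depends on it. From the documents: n = 2,200 per arm (SAP 2.5), 1 to 3 periods (Protocol 6.6) and a 5% significance level. Assumed: the same risk q per period in both arms; a proportion c continuing; each participant-episode in the sample size is one enrolment; and n (%) in Table 6a counts enrolments that ever report the symptom.

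**Probability of ever reporting a symptom.** Two simple continuation models:
- A, one or three periods: P = (1−c)q + c[1−(1−q)³]
- B, a decision after each of the first two periods: P = (1−c)q + c(1−c)[1−(1−q)²] + c²[1−(1−q)³]

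**Chance of a significant result towards the arm with less continuation** (nominal 2.5% in that direction), where p̄ is the mean of P₁ and P₀:

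Φ{ [ |P₁−P₀| − 1.96√(2p̄(1−p̄)/n) ] / √([P₁(1−P₁)+P₀(1−P₀)]/n) }

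Example, model A, q = 10%, c = 40% v 60%: P = 0.1684 v 0.2026, difference 0.0342. The critical difference is 1.96 × 0.01172 = 0.0230, and (0.0342 − 0.0230)/0.0117 = 0.96, so Φ = 0.83.

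| q | Continuing | Model A | Model B | Chance |
|---|---|---|---|---|
| 10% | 50% v 50% | equal | equal | nominal |
| 10% | 50% v 55% | 18.55% v 19.4% | 16.5% v 17.4% | 11–12% |
| 10% | 40% v 50% | 16.8% v 18.55% | 14.9% v 16.5% | 32% |
| 10% | 40% v 60% | 16.8% v 20.3% | 14.9% v 18.3% | 83–86% |
| 5% | 40% v 60% | 8.7% v 10.6% | 7.6% v 9.5% | 55–59% |
| 2% | 50% v 55% | 3.9% v 4.1% | 3.5% v 3.7% | 5% |
| 2% | 40% v 50% | 3.6% v 3.9% | 3.1% v 3.5% | 10% |
| 2% | 40% v 60% | 3.6% v 4.3% | 3.1% v 3.9% | 26–29% |

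Fisher's exact test would give slightly lower chances. Clustering from re-enrolment is ignored.

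**Does stopping because of an AE create the bias?**
- *Stopping for the symptom being counted: no.* With q = 10% and 60% of symptom-free people continuing at each decision, P = 0.1 + 0.9×0.6×0.1 + 0.9²×0.6²×0.1 = 18.3%. The proportion continuing after the symptom does not enter the formula.
- *Stopping for a different symptom: yes.* Suppose 20% have some other AE in each period, independently, and continuation falls from 60% to 10% after one. Average continuation is 0.8×0.6 + 0.2×0.1 = 50%. The percentage for a symptom with 10% risk per period falls from 18.3% to 16.5%, because later chances to report it are lost.

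**After the fix.** In the first period each arm shows q, here 10% v 10%, whatever the continuation.

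**The case against.** **A stronger reading that does not hold.** A reader might infer that people made unwell by AL stop, so the AL arm would show fewer AEs and the table would point the wrong way. The documents do not support this. An AE recorded before stopping stays in the numerator, and the calculation above gives 18.3% however many of those people continue. The bias needs continuation to differ for reasons unrelated to AEs, or one symptom to remove later chances to report others.

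**The size is assumed.** This stands. A gap of 40% v 60% is large. If 60% of AE-free people continued, the AE risk were 10% and everyone with an AE stopped, continuation after the first period would fall only to 0.9×0.6 = 54%. Smaller gaps give the smaller figures in the table, and rare events such as SAEs would be little affected. AEs confined to the first days of dosing would also be less affected, since everyone shares that exposure.

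**Continuation formally follows a forest plan, not a choice about the drug.** This also stands: a difference between arms is possible but not built into the design.

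**Other routes to detection exist.** Participants may report symptoms between visits, and Protocol 6.13 asks investigators to continue study procedures after AEs or non-compliance. These soften the problem, but they do not give further questionnaires to people who declare no return.

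**The counting unit is not defined.** Neither document defines n or N in Table 6a. Counting enrolments that ever report is the natural reading, supported by the highest-grade heading in Table 6b. If N were follow-up periods, unequal numbers of periods would not by themselves shift the percentages. This is a reason to define N, not a reason to leave the table as it is.

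**Conclusion.** The point holds in a conditional form. As planned, the row percentages and p-values in Table 6a compare arms over observation periods that can differ after randomisation, and the safety section of the SAP contains no adjustment or period split that would reveal it. If continuation is equal in the two arms there is no bias. If it differs, the effect on a common symptom runs from small (about 11–12% chance of a spurious significant result for a 5-point gap at 10% risk per period) to serious for a 20-point gap, and is less for rarer symptoms. These sizes rest on assumed risks and continuation rates, a constant risk per period, and a count of enrolments ever reporting. The documents do not show that continuation will differ, nor in which direction. The reason to act is that the comparison can be protected in advance at little cost.

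**What to change.** In SAP 4.4.5 and Table 6a:
1. Add a first-period comparison (D0 to D28–35), where every enrolment is due one post-dose questionnaire, and make it the between-arm AE comparison, with risk differences and 95% confidence intervals.
2. Report periods 2 and 3 per period at risk, or per person-time, with the number at risk in each arm. Label them descriptive, because those who continue are a selected group.
3. Tabulate periods on study and questionnaires completed by arm, including attendance at the first visit, on which item 1 depends.
4. Keep the overall n (%) as a descriptive summary.
5. Define n and N (participant, enrolment or period), and reconcile the two AE windows in SAP 4.4.5.

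The cost is SAP wording and a re-cut of data already planned for collection; no study procedure changes. The downside is that later-period events are described rather than formally compared.

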5.4.2. Secondary Endpoints

1. 28-day, 56-day and 84-day PCR *Plasmodium* positivity rate for each *Plasmodium* species

2. Proportion of participants with confirmed malaria reported between day 0 and day 28 for each species
3. Description of epidemiological situation of malaria in the study areas from passive surveillance data.
4. Prevalence of *Kelch13* mutations and other genetic markers of antimalarial drug resistance of known functional significance.
5. Incidence of adverse events and serious adverse events by study arms during the course of prophylaxis.
6. Data on the place of residence, work, recent travel history and mobile phone use.
7. Detailed data and GPS mapping on a subset of participants and their peers relating to the behaviours and risk factors associated with malaria infection.
8. Overall prevalence of Plasmodium at baseline, stratified by season and risk factors.
9. Day 0, 28, 56 and 84 capillary blood levels of lumefantrine.
10. Prevalence of serological diagnostic markers of other infectious diseases.

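### SAP Tables 6a to 6c list 13 fixed symptoms with no any-AE, other or diagnosis row, so they do not deliver the all-AE summary that the SAP promises

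*SAP*

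**What the plan says.** The endpoint, secondary endpoint 5 in protocol section 5.4.2, is "Incidence of adverse events and serious adverse events by study arms during the course of prophylaxis". Protocol section 9.2.3 adds that the frequencies of AEs and SAEs will be compared between arms with Fisher's exact test.

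Protocol section 8 sets the recording rule: "Whenever possible, the adverse event should be evaluated and reported as a diagnosis rather than as individual signs or symptoms". Symptoms are the fallback: "If a definitive diagnosis is not possible, the individual symptoms and signs should be recorded". The destination is one form: "All adverse events must be recorded in the AE/SAE CRF". A separate instrument supports the detection of AEs: "A symptom questionnaire will be performed on enrolment and at each subsequent follow-up visit to the health care center, to aid in the identification of" such events.

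SAP section 4.4.5 sets the scope of reporting: "AE summaries will be generated for all AEs that occurred after study drug administration, until the end of the study". It then names the tables: "Incidence of adverse events and serious adverse events by study arms during the course of prophylaxis will be presented in the table 6a below", with intensity in Table 6b and relationship to study drug in Table 6c.

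**The concern.** The plan has three parts that should fit together: how an event is written down, which events are to be summarised, and which rows exist to hold them. The first prefers diagnoses and the second covers every AE, but the third holds only symptoms from a closed list, plus SAEs in one table.

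The safety comparison is at stake. The protocol says AEs are reviewed in order to add to the evidence on artemether-lumefantrine as prophylaxis. For that purpose a reader will first look for the proportion in each arm with at least one AE, and then for what those events were. The shells supply neither in full, and events entered in the protocol's preferred form are the ones most likely to have no row.

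**Working it through.** There is no stated figure to reproduce, since the point depends on no sample size or event rate. The check is a row count set against the text.

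**Step 1: rows in the shells.**

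| Table | Symptom rows | SAE row | Any-AE row | Other or diagnosis row |
|---|---|---|---|---|
| 6a (incidence) | 13 | 1 | 0 | 0 |
| 6b (severity) | 13 | 0 | 0 | 0 |
| 6c (relatedness) | 13 | 0 | 0 | 0 |

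The 13 are headache, loss of appetite, dizziness, fatigue, joint pain, muscle pain, abdominal pain, nausea, vomiting, diarrhoea, itching, cough and fever. In Table 6a they stand under the heading "Signs and symptoms". All three lists are closed. SAP Table 1, by contrast, uses open-ended rows for occupation, drug history and medical history. The SAP names no coding dictionary and gives no rule for mapping a diagnosis to a symptom row.

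**Step 2: what the protocol counts as an AE.** Protocol section 8.1.1 includes physical signs, abnormal laboratory results and illnesses as well as symptoms. Following each kind of event into the tables gives:

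- Non-serious illness recorded as a diagnosis: no row in 6a, 6b or 6c.
- Non-serious symptom outside the 13: no row. Protocol section 12.4.2 itself names unpleasant taste as a multivitamin side effect, and no row is labelled for it.
- SAE that is not one of the 13: counted in 6a, with no row in 6b or 6c. Table 6b has columns for life-threatening and fatal events, but its only rows are the 13 symptoms.
- Confirmed clinical malaria: counted as efficacy, within the outcome of Tables 2 and 3, and not as an AE.

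**Step 3: whether overall incidence can be recovered from Table 6a.** Let p1 to p13 be the proportions in the symptom rows, s the proportion with an SAE, and u the proportion with an AE that has no row. One person can appear in several rows, so

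max(p1, ..., p13, s) ≤ proportion with any AE ≤ min(1, p1 + ... + p13 + s + u).

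The table gives the lower limit. It does not give u, so it gives no usable upper limit. Secondary endpoint 5, read as the proportion with at least one AE by arm, cannot be derived from the table.

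**Step 4: size.** The documents give neither an expected AE rate nor a share of AEs expected to be entered as diagnoses. The number of events without a row therefore cannot be estimated.

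**The case against.** The strongest reply is that these are only table shells and that the text governs. SAP section 4.4.5 promises summaries for all AEs, and protocol section 9.2.3 promises a comparison of AE frequency and a description of clinically relevant abnormalities. On this view nobody decided to omit events, and the shells simply lag behind the text. That is a fair account of the cause. It does not remove the conflict, because the SAP names Table 6a as the place where incidence is presented, and a programmer working from the shells would produce no total.

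A second reply is that the symptom questionnaire is completed at enrolment and at each follow-up visit. If the 13 rows are filled from it, a headache or cough is counted whatever diagnosis stands on the AE form. This stands in part. The SAP does not say which form feeds the tables, and the case record form is not among the documents, so some diagnosed illnesses may well show up as symptoms. The diagnoses themselves, and events without any of the 13 symptoms, would still have no row.

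A reader might also infer that differing symptom lists in Tables 1 and 6a leave treatment emergence without a baseline. That does not follow, because emergence is judged per participant from the enrolment record and needs no matching row in a summary table.

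**Conclusion.** The mismatch is real and can be verified by counting rows. As drawn, the tables do not report overall AE incidence by arm. Non-serious AEs recorded as diagnoses or as unlisted symptoms have no row in any AE table, and SAEs outside the 13 symptoms have no row for severity or relatedness. The conclusion rests on taking the shells as drawn. The effect is confined to safety reporting; the primary analysis is untouched.

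Three stronger readings are tempting, and the documents support none of them:

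- That AE incidence is understated. No total is shown, so none is understated. It would be so only if the listed rows were taken as the full count and unlisted events occurred.
- That diagnosed events appear nowhere. Confirmed malaria does appear, as efficacy, in Tables 2 and 3.
- That open-label recording habits would create a false difference between arms. Nothing in the documents suggests that staff would enter diagnoses more often in one arm than in the other, and any size put on it would rest on invented rates.

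**What to change.** In SAP section 4.4.5:

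- Add to Tables 6a, 6b and 6c a row for any AE, stating whether the count is of participants or of episodes with at least one.
- Add to the same tables rows for other and diagnosed AEs, listed by term.
- Add an SAE row to Tables 6b and 6c.
- State that these rows are filled from the AE/SAE case record form. If the 13 symptom rows come from the symptom questionnaire, label them as such.

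The cost is a few extra table rows and some coding of AE terms. No change to the case record form is needed, because the protocol already requires every AE to be entered on the AE/SAE form.
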